To compare the absorption and activity of guercetin or isoguercetin with or without ascorbic acid, we will perform pharmacokinetic and pharmacodynamic analysis in 4 cohorts. Cohorts A, B, and C will consist of 10 healthy adults and cohort D will consist of 20 participants with positive anti-phosphololipid anitbodies or myeloproliferative disorder. Group A will include 10 healthy individual receiving oral chews containing quercetin (500 mg total). Subjects may return and given chews containing quercetin (500 mg) in combination with ascorbic acid (500 mg) and niacin (20mg). Group B will include 10 healthy adults with isoguercetin (500 mg) alone and isoguercetin (500 mg) with ascorbic acid (500 mg) with niacin (20mg). Group C will be comprised of 10 healthy adults receiving isoquercetin (1000 mg) alone and isoquercetin (1000mg) with ascorbic acid (1000 mg) with niacin (40mg). Group D will include 20 individuals with antiphospholipid antibodies or myeloproliferative disorder receiving isoguercetin (1000 mg) with ascorbic acid and niacin. Group E will be comprised of 10 healthy individuals who will receive isoguercetin 1000 mg with ascorbic acid 248 mg and niacin 20 mg in a capsule formulation. For group A, B, C and E blood will be drawn prior to the administration of study drug and at different time points over a 24-hour period (0 min, 30 min and 1, 2, 4, 6, 8, and 24 hours) in order to assess pharmacokinetics and pharmacodynamic inhibition of PDI activity. Group D will have blood drawn prior to the administration of study drug and 4 hours following the administration of the study drug in order to assess pharmacodynamic inhibition of PDI activity.

Group A will receive 2 chews, each containing:

1) quercetin 250mg

2) quercetin 250mg, vitamin c 250mg, niacin 10mg

Group B will receive 2 chews, each containing 3) isoquercetin 250mg,

4) isoquercetin 250mg, vitamin C 250g, niacin 10mg

Group C will receive 4 chews, each containing

5) isoquercetin 250mg,

6) isoquercetin 250mg, vitamin C 250g, niacin 10 mg

Group D will receive 2 chews, each containing 7) isoquercetin 500 mg, vitamin C 500g, niacin 20mg

Group E will receive 4 capsules, each containing 8) isoquercetin 250mg, vitamin C 62mg, niacin 5mg

All study drugs will be provided by Quercegen Pharma.

Study Procedures: Healthy participants (Group A, B, C and E)

- 1. Register patient at the Clinical Research Center (CRC) facility at BIDMC.
- 2. Urinary pregnancy test (if applicable)

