Microparticles will be isolated from PFP and PDI activity on the surface of plasma microparticles will be measured with a fluorescent substrate (dieosin glutathione disulfide or di-E-GSSG) per previously described methods (Raturi et al Biochimica et Biophysica Acta 2008;1778:2790-2796.

Additional hemostasis-related assays such as microparticle and tissue factor activity will be performed using PFP.

В.	Statistical Considerations

a. **Sample Size Justification:** A total of 40 healthy individuals will be enrolled in the trial. Data collected from the pharmacokinetic analysis will be used to identify the formulation of study drug, either isoquercetin or quercetin with or without ascorbic acid. Ten patients per group is the minimum number necessary to establish a difference in values of pharmacologic variables (e.g. Cmax or AUC) of at least one standard deviation of magnitude with a 0.05 level of significance using a paired two-tailed test of log-transformed values. Although this study may be technically underpowered to detect small differences, a clinically significant difference between the relative bioavailability among the four formulations should be readily apparent. If a subject chooses not to participate in the second part of the study (i.e. quercetin in combination with ascorbic acid and niacin) then alternative subjects will be recruited to complete the second PK/PD analysis.

For the cohort with antiphospholipid antibodies or myeloproliferative disorder, we plan to enroll 20 patients (approximately 10 in each arm). The null hypothesis is there is no difference in thrombin-induced thrombin generation measured at 0 and 4 hours. The sample size calculation is based on preliminary data demonstrating that the mean decrease in thrombin generation before and after isoquercetin was -54% with a

standard deviation of mean % difference of .41 in healthy individuals. Accordingly, using a paired t-test analysis for time 0 and 4 hours with a 2-sided alpha of 0.05, the power of the study is 95.8

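### If anyone declines part two, the replacement rule as it reads refills the session but not the pair on which the sample size of ten rests

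*Combined protocol and SAP*

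**What the plan says.** All the sizing for the healthy groups is in one paragraph, the Sample Size Justification (section B3.B.a). Ten per group is described as the minimum for a difference "of at least one standard deviation of magnitude with a 0.05 level of significance using a paired two-tailed test of log-transformed values". No power is stated, and the plan does not say which SD is meant.

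The paragraph then deals with non-return. The case it covers is worded "If a subject chooses not to participate in the second part of the study (i.e. quercetin in combination with ascorbic acid and niacin"). The action it prescribes for that case is "then alternative subjects will be recruited to complete the second PK/PD analysis". Overall Design (section B3.A) makes the return visit optional for Group A: "Subjects may return and given chews containing quercetin (500 mg) in combination with ascorbic acid (500 mg) and niacin (20mg"). The descriptions of Groups B and C list two treatments each, without that wording.

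The paragraph also gives the data a second use. They "will be used to identify the formulation of study drug, either isoquercetin or quercetin with or without ascorbic acid". On that choice it first concedes a limit ("Although this study may be technically underpowered to detect small differences") and then expects all the same that "a clinically significant difference between the relative bioavailability among the four formulations should be readily apparent". Under Overall Design quercetin is given only in Group A ("Group A will include 10 healthy individual receiving oral chews containing quercetin (500 mg total")) and isoquercetin in the other groups.

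The Data Analysis section (B3.B.b) lists the PK quantities. It names no method for partly paired data and no test for PK differences between groups.

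**The concern.** A paired test uses only people measured under both treatments. A subject who leaves after part one and a newcomer who attends only part two supply one value each, from different people. The rule brings the number of part-two sessions back to ten but leaves the number of pairs short. Because the plan calls ten the minimum, there is no spare pair. The contrast affected is the primary question in section B1, whether ascorbic acid and niacin increase absorption.

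A smaller point concerns scope. The only sizing figure is for a paired comparison, yet the same paragraph uses the data to choose between compounds that Overall Design gives to different people. A reader could carry the 1-SD figure over to that choice, where it does not apply.

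**Working it through.** **Inputs.** From the Sample Size Justification: n = 10 per group, difference 1 SD on the log scale, two-sided alpha 0.05, paired test. Assumed, because not stated: an 80% power target, and that the SD is that of the paired log differences.

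**Step 1, the plan's own figure.** Power = P(T > t), where t is the 97.5% point of Student's t with n − 1 df, and T is noncentral t with n − 1 df and noncentrality d√n. With d = 1 and n = 10, the noncentrality is 3.162 and t = 2.262, so power is 80.3%. Nine pairs give 74.8%, so ten is the smallest number that reaches 80%. The plan's figure reproduces.

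**Step 2, lost pairs at 1 SD of the differences.**

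| Complete pairs | Noncentrality | Critical t | Power |
|---|---|---|---|
| 10 | 3.162 | 2.262 | 80.3% |
| 9 | 3.000 | 2.306 | 74.8% |
| 8 | 2.828 | 2.365 | 68.1% |
| 7 | 2.646 | 2.447 | 60.0% |

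**Step 3, if the SD is between-subject instead.** Then d = 1/√(2(1 − ρ)), where ρ is the within-person correlation. The documents give no ρ, so a range is shown.

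| ρ (assumed) | d | Ten pairs | Seven pairs |
|---|---|---|---|
| 0.3 | 0.845 | 66.3% | 46.7% |
| 0.5 | 1.000 | 80.3% | 60.0% |
| 0.7 | 1.291 | 95.1% | 81.1% |
| 0.8 | 1.581 | 99.3% | 93.3% |

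The loss is small when correlation is high and substantial when it is not.

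**Step 4, quercetin v isoquercetin at equal dose (Group A v Group B).** These are two independent groups of ten. With one session per person and a difference of 1 between-subject SD, the noncentrality is 1/√(2/10) = 2.236 on 18 df, with critical t = 2.101. Power is 56.2%. Solving for 80% power gives a detectable difference of 1.32 SD.

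**The case against.** **The text does not bar a replacement from taking both parts, and nobody may decline.** Both are true. The natural reading of the sentence is part two only, but it does not list the replacement's sessions. The rule's parenthesis names only the quercetin product, so it may reach one group only. This makes the loss conditional. It does not remove the need to say what is meant.

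**The expected effect may be well above 1 SD.** Section B2 reports about 1.5 µM after quercetin 375 mg twice daily and close to 5 µM after 500 mg with the additives. The ratio is 5/1.5 = 3.3. Scaled linearly for dose it is 5/(1.5 × 500/375) = 2.5. The logs are 1.20 and 0.92. If the SD of paired log differences is 0.5 to 0.7 (assumed), the effect is 1.3 to 2.4 SD, and seven pairs give 82% to above 99% power. At SD 0.9 with the scaled ratio, they give 62%. These are cross-study figures with different dosing, so they are indicative only. The objection stands as a limit on the size of the harm.

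**The plan does not claim to power quercetin v isoquercetin.** A reader might infer that it does, because the choice of compound and the 1-SD figure share a paragraph. The documents do not support that reading: the figure is tied to a paired test, and the remark that a difference should be readily apparent is not a power claim. A reader might also infer that the wrong compound is likely to be chosen. That does not follow either. At a true difference of 1 between-subject SD, the higher of two single-session means of ten is the right one with probability Φ(1/√0.2) = Φ(2.236) = 98.7% under a normal model. What remains is that the caveat about small differences does not cover 1 SD, the very difference used for sizing, and that no figure is given for the unpaired comparison.

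**The unpaired comparison may have no object.** Section B1 says the first 30 healthy subjects receive isoquercetin chews, which would leave no quercetin group. This stands, and the two sections must be reconciled first.

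**Conclusion.** The point holds in a limited form and is minor. Ten per group is right for ten complete pairs. Followed as it naturally reads, the replacement rule costs one pair for each subject who declines part two. At 1 SD of paired log differences, power goes from 80.3% to 74.8%, 68.1% and 60.0% with one, two and three pairs lost. This rests on the assumed 80% target, on the SD being that of the differences, and on someone declining. The documents do not show that a loss will occur, or that the rule extends to Groups B and C.

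The scope point is secondary. The paired figure applies only to the with/without contrasts inside a group. For Group A v Group B the comparable figure is 56.2% power at 1 between-subject SD, provided Group A does receive quercetin.

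**What to change.** **Main change.** Replace the replacement sentence with, for example: *A subject who does not take part in the second part will be replaced by a new subject who completes both parts, until ten subjects have completed both in each group given two treatments; data from the subject who left are kept.* State which groups this covers. The cost is one extra PK session per replacement (21 sessions instead of 20 in a group with one decliner whose replacement completes both parts), and nothing if nobody declines.

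**Secondary change.** Say that the 1-SD statement covers only the within-group with/without contrasts, and name the SD and the power. Reconcile section B1 with Overall Design on whether a quercetin group exists. If it does, report Group A v Group B for AUC and Cmax as a geometric mean ratio with 95% CI, and note the 1.32 SD detectable difference for one session per person. This is wording only; its price is a less favourable stated figure for that comparison. No larger sample is asked for.

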PART B STUDY DESCRIPTION

TITLE OF PROTOCOL	Pharmacokinetic and pharmacodynamic study of oral quercetin and isoquercetin in healthy adults and patients with hypercoagulable states.
Principal Investigator	[name]

B1. PURPOSE OF PROTOCOL

The primary goal of this trial is to perform a pharmacokinetic analysis in 60 healthy individuals of quercetin or isoquercetin and determine whether the addition of ascorbic acid and niacin increases absorption. The secondary goal is to evaluate the pharmacodynamic activity of quercetin or isoquercetin metabolites to inhibit protein disulfide isomerase activity. The first 30 patients in this group will receive isoquercetin delivered in the form of a chew. An additional 10 patients will receive isoquercetin delivered in capsule form. Pharmacodynamic studies will also be performed in an additional cohort of 20 patients with evidence of antiphospholipid antibodies or myeloproliferative disorder.

B2. SIGNIFICANCE AND BACKGROUND FOR THE STUDY

Extracellular disulfide isomerization has been explored as a regulatory pathway in platelet activation and fibrin generation. Protein disulfide isomerase (PDI) is a thiol isomerase that is secreted by platelets and endothelial cells following activation and localizes to the membrane surface. The hemostatic targets of extracellular PDI continue to be elucidated and may include tissue factor and platelet integrins such as IIbIIIa. The [name] Laboratory recently demonstrated the critical role of extracellular PDI in regulating platelet thrombus formation and fibrin deposition in vivo. Employing intravital fluorescence microscopy to monitor a laser-induced vascular injury in mice, we observed that inhibition of PDI with either bacitracin, a non-specific thiol isomerase inhibitor, or a specific and inhibitory monoclonal anti-PDI antibody completely blocked both platelet thrombus formation and fibrin generation is not unique to the laser injury model as similar observations have been made using carotid artery ligation and ferric chloride injury in mice ([name], [name] and [name], unpublished results).

Identification of quercetin as a potent inhibitor of PDI

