of quercetin at 375mg daily twice daily, the IC50 achieved was only 1.5uM. Recent data provided by Quercegen Pharma suggests that quercetin (500mg) in combination with ascorbic acid and niacin improves both stability and absorption, yielding serum concentrations close to 5uM. Quercegen Pharma formulates quercetin in chews containing ascorbic acid but formal PK studies are lacking. Also, the presence of a glucoside moiety at the 3 position of isoquercetin appears to increase absorption possibly through a sodium-dependent glucose transporter on enterocytes. Quercetin glucosides such as quercetin-3-rutinoside or isoquercetin undergo deglycosylation locally at the enterocyte to yield the aglycone. Although the absorption of the related quercetin compounds may differ, all forms of quercetin are metabolized in the enterocyte and liver and circulate as similar glucuronated, sulfated, and methylated conjugates. These conjugates have demonstrated biologic activity and in preliminary experiments using an insulin turbidometric assay we observed that purified quercetin-glucoronide inhibited PDI activity with greater potency than quercetin or quercetin-3-rutinoside.

In summary, we previously observed that inhibition of PDI in vivo inhibits platelet thrombus formation and fibrin generation in a mouse thrombosis model. Following the identification of quercetin and related flavonoids as potent PDI inhibitors in vitro, we demonstrated antithrombotic efficacy in animal models as well as a reduction in d-dimer in humans. Based on these preliminary findings and unique antithrombotic mechanism of PDI inhibition, we propose to evaluate quercetin as an antithrombotic in specific patient populations. Prior to initiating these trials, we plan to perform a pharmacokinetic and pharmacodynamic study to evaluate the influence of ascorbic acid and niacin on quercetin/isoquercetin absorption. As planned trials include patients at risk of thrombosis such as those with elevated antiphospholipid antibodies, will explore pharmacodynamics specifically in this population.

B3. DESCRIPTION OF RESEARCH PROTOCOL

A. Study Design – Overview, Methods, Procedures

Overall Design

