b. **Data Analysis:** The concentration of quercetin in plasma will be determined by liquid chromatography and mass spectrometry in collaboration. Analysis will include elimination half-life, peak concentration, and area under the curve. We will also evaluate an experiment assay to monitor PDI inhibition in plasma using a dieosin glutathione disulfide (di-E-GSSG) to liberate a self-quenching N-terminal GSSG residue following cleavage of a disulfide bond. There is a planned comparison of peak PDI inhibition for the different groups and correlation with serum quercetin levels. Statistical analysis will be performed in collaboration with [name] and [name] at DFCI.

C. Subject Selection

Inclusion Criteria

- 1. Subject is willing to participate and provide informed consent
- 2. Subject is considered reliable and capable of adhering to the protocol per the judgment of the Investigator
- 3. Subjects in group D must exhibit good organ reserves (within prior 4 weeks) defined as:
- a. Estimated GFR >35 (formula),
- b. Platelet count >65 K/uL,
- c. Hemoglobin >10.5 grams/dL
- d. Total bilirubin <2.0 mg/dL
- 4. Minimum age 18 years old
- 5. Body mass index (BMI) between 18 and 35 kg/m2
- 6. For cohort D (antiphospholipid antibodies or myeloproliferative disorder)

a. Subjects in group D with antiphospholipid antibodies must have at least one positive antiphospholipid antibody within the last 8 weeks and/or previous confirmed antibodies (2 or more occasions at least 12 weeks apart) :

i. Positive lupus anticoagulant

- ii. anticardiolipin antibody IgM or IgG (>40U GPL)
- iii. anti- β 2 Glycoprotein1 antibody titer (>35 units)

b. Subjects in cohort D with myeloproliferative disorder must have confirmed diagnosis of essential thrombocythemia or polycythemia vera through bone marrow biopsy or molecular testing.

Exclusion Criteria

1. Pregnant. If female of child-bearing age, negative urinary pregnancy test prior to dosing of quercetin or isoquercetin

2. No history of malabsorptive gastrointenstinal disorder

3. Currently taking, warfarin, low-molecular weight heparin or other anticoagulants (such as direct thrombin inhibitors or factor X inhibitors)

- 4. Prescribed niacin for hyperlipidemia
- 5. Known HIV

6. History of sensitivity or intolerance to flavonoids, niacin or ascorbic acid

7. May not have uncontrolled intercurrent illness including, but not limited to ongoing or

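### Does Group D's thrombin-generation hypothesis go untested because Data Analysis does not repeat it?

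*Combined protocol and SAP*

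**What the plan says.** The protocol speaks of Group D's pharmacodynamic work in several places.

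- **B1, Purpose:** "Pharmacodynamic studies will also be performed in an additional cohort of 20 patients with evidence of antiphospholipid antibodies or myeloproliferative disorder". This is not limited to PDI, although B1 describes the secondary goal in terms of PDI inhibition.
- **B2, closing paragraph:** the study "will explore pharmacodynamics specifically in this population", referring to patients at risk of thrombosis such as those with antiphospholipid antibodies.
- **B3.A, Overall Design:** Group D has blood drawn before dosing and "4 hours following the administration of the study drug in order to assess pharmacodynamic inhibition of PDI activity".
- **B3.A, Plasma sample preparation and storage:** after quercetin quantitation and the microparticle PDI assay, "Additional hemostasis-related assays such as microparticle and tissue factor activity will be performed using PFP".
- **B3.B.a, Sample Size Justification:** "we plan to enroll 20 patients (approximately 10 in each arm"). Then: "The null hypothesis is there is no difference in thrombin-induced thrombin generation measured at 0 and 4 hours". The test is a paired t-test, two-sided alpha 0.05. The inputs are a mean change of -54% with SD 0.41, from healthy individuals. The stated power is 95.8.
- **B3.B.b, Data Analysis:** half-life, peak concentration and AUC, then "We will also evaluate an experiment assay to monitor PDI inhibition in plasma", then "There is a planned comparison of peak PDI inhibition for the different groups and correlation with serum quercetin levels".

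**The concern.** Group D has one formal hypothesis, and it concerns a variable named only in the sample-size paragraph. The design section gives a different variable as the reason for the draws, and the analysis section omits both the variable and the test. A reader who takes Data Analysis as the full list would not test the hypothesis on which the cohort was sized. A reader who takes the purpose sentence as naming the endpoint would report PDI inhibition, for which no effect, SD or power is given. If both readings were open, the Group D result could be chosen after the data were seen.

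The power figure raises a related doubt. It is called the power of the study, for a cohort of 20, but it may refer to one diagnosis only. The plan does not say outright whether the test pools the two diagnoses or is run in each.

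**Working it through.** **1. Reproduce the stated power.** The inputs come from the Sample Size Justification: mean change 0.54, SD of the change 0.41, about 10 patients per arm, paired t-test, two-sided alpha 0.05. No dropout is stated and none is assumed.

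- Standardised effect: d = 0.54/0.41 = 1.317.
- Noncentrality: d × √n, with n − 1 degrees of freedom; power from the noncentral t distribution.

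| n | Noncentrality | Power |
|---|---|---|
| 9 | 3.951 | 93.1% |
| 10 | 4.165 | 95.83% |
| 11 | 4.368 | 97.5% |
| 20 | 5.890 | 99.98% |

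Only n = 10 gives 95.8. Other methods at n = 10 do not match: one-sided paired t, 98.55%; normal approximation, 98.63%; two-sample t with 10 per arm, 79.5%. The figure is therefore a correct within-patient calculation for one diagnosis of about 10, and it agrees with the text just before it. The sentence breaks off after 95.8 with no percent sign or full stop, so a qualifier may have been lost when the text was extracted. The label should not be pressed.

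**2. Is the Group D test specified?** Paragraph a of Statistical Considerations supplies every element needed to run it:

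- variable: thrombin generation;
- contrast: 0 versus 4 hours within patient;
- test: paired t;
- alpha and sides: 0.05, two-sided.

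The Group D procedures collect 20 ml at exactly those two times, so the draws fit the test.

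**3. Is Data Analysis a complete list?** No. Paragraph a also states a paired two-tailed test of log-transformed Cmax or AUC for the healthy groups, and paragraph b does not repeat that either. Nor does it mention the platelet aggregation studies set out in B3.A. The two paragraphs divide the work: a holds the hypotheses and tests, b mainly the measurements. Leaving a test out of b does not withdraw it.

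**4. Does the purpose sentence set a rival endpoint?** The matching sentence for Groups A, B, C and E gives pharmacokinetics and PDI inhibition as the reasons for their draws. Yet the procedures also send samples to platelet aggregation and to other haemostasis assays. Such sentences are summaries. The Group D one carries no null hypothesis, test, effect or power for PDI. The open-ended list of additional assays leaves room for thrombin generation.

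**5. Does pooling matter?** On the plan's inputs, a per-diagnosis test has power 95.83% at 10 patients, and a pooled test has 99.98% at 20. A split of 9 and 11 gives 93.1% and 97.5%. Power is adequate under either reading.

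**The case for a change.** The strongest case is that a sample-size rationale does not by itself designate an endpoint, least of all when the design section names another variable and the analysis section is silent. The PDI comparison between groups does not fill the gap: it is a different variable and a different contrast, and Group D, with one post-dose sample, has no observed peak to set beside the serially sampled groups. No thrombin-generation assay is named in the laboratory procedures. If testing is per diagnosis, two tests at 0.05 carry a 1 − 0.95² = 9.75% chance of at least one false positive, and power for both to succeed is 0.958² = 91.8% (both assuming independence), with no rule for reading them together.

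Part of this stands. The assay is not described, the purpose sentence is incomplete, and pooled versus per-diagnosis testing is left to inference.

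The rest does not carry. The sample-size paragraph is the only place where a Group D hypothesis is stated, and it is stated in full, so there is no second prespecified hypothesis to switch to. The two-test figures matter only for a joint claim, which the plan never makes; B2 describes this work as exploratory. The healthy-volunteer source of the effect and SD is already disclosed in the sentence just before the power figure. The assay cannot be wholly new to the investigators, since the sizing rests on preliminary thrombin-generation data.

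**Conclusion.** No change is called for. The gap is one of cross-reference between neighbouring paragraphs, and analysts would fill it sensibly. Someone working from Statistical Considerations as a whole would run the paired 0 versus 4 hour test on thrombin generation and report PDI inhibition alongside it. The stated 95.8 is right for about 10 patients per diagnosis (95.83%), and pooling would only raise it, to 99.98%. No stated figure is wrong, and neither the cohort size nor the sampling times are affected. Repeating the test in Data Analysis, naming the assay, widening the purpose sentence and saying whether the diagnoses are pooled would make the text tidier, but they record detail and correct no unsound analysis.

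This rests on three assumptions: that the two paragraphs are read together; that the effect and SD from healthy individuals carry over to patients, as the plan itself assumes; and that the Group D samples suffice for the assay, whose sample type and volume the document does not give.
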